The purpose of the study is to test the question of: Does the addition of 0.5ml 1% lidocaine compared to 0.5 ml normal saline solution to 1.2 million units of benzathine penicillin G affect the pain experienced by individuals being treated for Treponema pallidum (syphilis) infections at 10 minutes and 24 hours post injection?

B Background

B1 Prior Literature and Studies, and Rationale for this Study

There is evidence to suggest that lidocaine can help reduce the pain associated with intramuscular injections of benzathine penicillin G or bicillin, used to treat syphilis

infections. A study published in the Journal of Pediatric Infectious Diseases in 1998 found that the use of lidocaine as a diluent of BPG significantly reduced the pain of injection. Another study by Estrada et al in 2019 looked at the addition of 1% mepivicaine as diluent for PGB vs PGB alone and showed that mepivicaine significantly decreased pain experienced by participants. Per the IUSTI European Guidelines for Syphilis management, lidocaine is used as a diluent for benzathine penicillin G since 1998. No studies have been performed thus far looking at prefilled benzathine penicillin G syringes and the possibility of inserting lidocaine to the injection to decrease the pain experienced by individuals being treated for syphilis infections, instead of using lidocaine as a diluent which is not possible for the BPG formulations present here in the US. in the US.

C Study Objectives

C1 Primary Aim

To see if there is any benefit of adding 0.5 ml 1% lidocaine to prepackaged Benzathine Penicillin G, with respect to pain, compared to standard of care, in the treatment of Treponema pallidum infections, both 10 minutes and 24 hours after injection.

C2 Secondary Aim

To see if there are any adverse effects of adding 0.5 ml 1% lidocaine to prepackaged Benzathine Penicillin G and to assess use of other pain medications 24 hours post injection.

D Investigational Agent

D1 Preclinical Data

1% lidocaine has been added as a solvent for BPG in other countries around the world.

D2 Clinical Data to Date

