Each log book entry will be entered into RedCap survey using the unique patient code and then the patient will fill out pain scale in RedCap using their unique code 10 minutes and 24 hours after injection through follow up email. If they do not respond to the 24 hour follow up email, a second email will be sent 48 hours after injection.

3.f Prior and Concomitant Therapy

Participants will be asked in the follow up survey about any other pain medications they have taken within the last 24 hours. They will also be asked about if this is their first treatment with respect to syphilis treatment, or if this is the second or third dose in a series of treatment. No other concomitant therapies would preclude individuals from participating in the study.

3.g Packaging

Both BPG syringes will look identical other than having one say L and one say R, based off randomization.

3.h Blinding of Study Drug

Both participants and clinicians will be blinded to the contents of the syringe. The nurse filling the syringe will assign the syringes randomly to be injected into L or R gluteal muscle and will label them accordingly, logging the designation in a log book that will remain blinded until the analysis portion of the study. The participant will be blinded as they will receive one site of injection with lidocaine and the other with normal saline, serving as their own intervention and control group.

3.i Receiving, Storage, Disposing and Return

BPG will be stored in the refrigerator in the Washington University St. Louis Infectious Diseases clinic, along with the lidocaine and normal saline solutions being kept in storage in the same clinic. All syringes will be disposed of in sharps containers, as well as used lidocaine ampules and normal saline syringes.

F Study Procedures

F1 Screening for Eligibility and Visit 1 (completed at one visit)

- 1- Participants with confirmed syphilis (RPR and treponemal test positive) who are receiving their first treatment injection of bicillin will be screened for participation in the study by infectious diseases clinicians, nurses, or Mas who interact with the patient during their injection visit. If patient is willing to participate, trial team will be notified. (15-30 minutes)
- 2- Trial team will assess patient for inclusion/exclusion criteria and ask if would like to be part of clinical trial. (5 minutes)

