- 3- The participant will then be taken to a clinic room and be shown the consent form. Study design will be explained to them including them receiving the same treatment they would normally but with one injection with 0.5 ml normal saline and one with 0.5 ml 1% lidocaine. They will then be asked if they have any questions and if they choose to consent, they will sign a physical consent form that will then be uploaded into their chart. (30-45 minutes)
- 4- Trial staff will then obtain the two injections and administer them one in each gluteal muscle. The patient will then be left for 15 minutes, after which they will fill out a pain score 0-10 for each injection site at 10 minutes post injection. (15-30 minutes)
- 5- Patient will then be informed they will receive an email survey (via RedCap) 24 hours

from trial staff to answer the same pain scale questions at that time. Exit counseling will occur and patient is then free to go. (15 minutes)

F2 Visit 2

Participants will receive an email from trial staff 24 hours after injection site to rate their pain from 0-10 at that time via online survey (RedCap) and to ask if any other pain medication was used in the last 24 hours and if they had any other symptoms/side effects. (5 minutes)

F3 Safety and Adverse Events

3.a Safety Monitoring

Patients will be asked about other side effects/adverse events during the 24 hour follow up. Patients can also contact providers through MyChart and/or through contacting the clinic/trial team.

3.b Medical Monitoring

i Investigator only

The investigator team will be monitoring the survey results for any signs of adverse effects. The monitoring will be ongoing and there will be an internal review of combined data every 6 months.

3.c Definitions of Adverse Events

Any undesirable experience associated with the use of medical product in patient. Common adverse events are listed above.

3.d Classification of Events

i Relationship

10 minutes after injection vs. 24 hours after injection

ii Severity

Mild, Moderate, or life threatening

iii Expectedness

Rare, other than injection site pain which is common

3.e Data Collection Procedures for Adverse Events

Adverse events will be asked about in the survey given 24 hours post injection.

3.f Reporting Procedures

Participants will report adverse events via a RedCap survey emailed 24 hours post injection. Other adverse events can be reported to PI or to clinic staff.

3.g Adverse Event Reporting Period

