Adverse events can be reported within 7 days post injection with participants having the ability to call for up to 7 days.

3.h Post-study Adverse Event

Any adverse event post study or the time listed above should be reported to the PI.

F4 Study Outcome Measurements and Ascertainment

The primary outcome measure will be pain rating scores from 0 (least pain) to 10 (most pain) at 10 minutes after injection in each injection site, as well as 24 hours after injection.

Secondary outcome measures will include adverse effects of lidocaine or benzathine penicillin G., such as allergic reactions or injection site reactions.

F5 Rationale for the Selection of Outcome Measures

Injection site pain is the most common adverse effect of Benzathine Penicillin G (BPG) intramuscular injections. For this reason, rating pain scales from 0-1 10 minutes and 24 hours after injection will allow us to measure immediate and longer term pain after injection, with and without lidocaine added to prefilled BPG syringes.

G Statistical Plan

G1 Sample Size Determination and Power

A sample size of 46 patients (92 injections) will be required to detect a clinically significant reduction in pain and discomfort associated with the injection of Bicillin, with a power of 80% and a significance level of 0.05.

G2 Interim Monitoring and Early Stopping

As this is a short term study with small population, it is not expected to stop early. Interim monitoring for adverse effects will occur at 6 months or after 24 participants have participated, whichever occurs first.

G3 Analysis Plan

Pain scores will be collected by trained study personnel. Data will be entered into a secure database and analyzed using statistical software. Descriptive statistics will be used to summarize the data, and t-tests or chi-squared tests will be used to compare pain scores and adverse effects between the treatment and control groups. They will also see if there any use of pain medications through descriptive statistics. Demographic data will also be collected.

G4 Statistical Methods

Descriptive statistics will be used to summarize the data, and t-tests or chi-squared tests will be used to compare pain scores and adverse effects between the treatment and control groups.

G5 Missing Outcome Data

Missing outcome data on follow up will be noted and statistical analysis will be performed on intention to treat model.

G6 Unblinding Procedures

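### Adverse events are actively asked about only once, at 24 hours, while the 7-day reporting period relies on participants coming forward; later site or allergic reactions are likely under-counted (minor)

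*Protocol*

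**What the plan says.** **Aim and outcome.** The secondary aim in Protocol C2 begins: "To see if there are any adverse effects of adding 0.5 ml 1% lidocaine to prepackaged Benzathine Penicillin G". Section F4 makes adverse effects of either drug a secondary outcome, "such as allergic reactions or injection site reactions". Sections G3 and G4 plan a comparison of adverse effects between treatment and control.

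**Solicited collection.** F3 3.e: "Adverse events will be asked about in the survey given 24 hours post injection". F3 3.a agrees: "Patients will be asked about other side effects/adverse events during the 24 hour follow up". F2 and F3 3.f describe the same single emailed survey. For non-responders, E3 3.e adds: "If they do not respond to the 24 hour follow up email, a second email will be sent 48 hours after injection". The on-site step in F1, shortly after the injections, is described as a pain score for each site. No symptom question is mentioned there.

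**Unsolicited collection.** F3 3.g: "Adverse events can be reported within 7 days post injection with participants having the ability to call for up to 7 days". F3 3.a adds: "Patients can also contact providers through MyChart and/or through contacting the clinic/trial team". F3 3.f also names the principal investigator and clinic staff as recipients of other reports.

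**The concern.** Safety is a stated aim with a planned comparison, so the way events are found matters. Up to the survey, every participant who answers has been asked about symptoms. After it, an event enters the data only if the participant decides to report it. A swelling at one site that appears on day 3 and is not volunteered leaves no trace.

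This is a matter of data collection, which the protocol fixes. An analysis plan cannot recover answers to a question that was never put.

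A related gap concerns side. Each participant receives both syringes, one on each side, so treatment and control can be compared for local reactions only if the side is known. The pain score is taken per site, but the symptom question in F2 is not said to ask for left or right.

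At stake is how far the trial can speak about tolerability after the first day, which matters because the benefits section (E2 2.e) looks ahead to a change in standard practice.

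**Working it through.** There is no figure in the plan to reproduce. The check has three parts.

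**1. Is there any later active question?** Setting the sections side by side:

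| Section | Time | Who starts the contact |
|---|---|---|
| F1 step 4 | on site, about 10 minutes | staff, but pain score only |
| F2, F3 3.a, 3.e, 3.f | 24 hours | trial staff, by survey |
| E3 3.e | 48 hours | trial staff, non-responders only |
| F3 3.g | to day 7 | participant |
| F3 3.a, 3.f (MyChart, clinic, trial team, principal investigator) | any time | participant |

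No section plans a solicited contact after these. F3 3.b has the investigators watch the survey results, which cannot contain an event that starts after the survey. F3 3.d sorts events into 10 minutes and 24 hours, so an event on days 2 to 7 has no category.

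**2. How much of the period is unsolicited?** Inputs: a reporting period of 7 days (F3 3.g), a survey at 24 hours (F3 3.e) and a reminder at 48 hours (E3 3.e).

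- Period: 7 × 24 = 168 hours.
- Answered at 24 hours: 168 − 24 = 144 hours; 144/168 = 0.857, or 6 of 7 days.
- Answered at 48 hours, and reporting everything up to then: 168 − 48 = 120 hours; 120/168 = 0.714, or 5 of 7 days.
- Answered neither email: no solicited safety data.

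These are shares of calendar time, not of events.

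**3. What could this do to detection? (illustration only)** The protocol gives neither the risk of an event after the survey nor the share that would be volunteered, so both are assumed. With 46 participants (G1), a later-event risk *p* and a captured share *f*, the chance of recording at least one event is 1 − (1 − *p f*)^46.

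| Assumed *p* | *f* = 1 | *f* = 0.5 | *f* = 0.25 |
|---|---|---|---|
| 1% | 0.370 | 0.206 | 0.109 |
| 2% | 0.605 | 0.370 | 0.206 |
| 5% | 0.906 | 0.688 | 0.439 |

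For *p* = 5% and *f* = 0.5: 1 − (1 − 0.025)^46 = 0.688. The table shows the direction and possible scale of the loss. It does not estimate it, and *f* = 1 is an upper limit that a day-7 survey with non-response would not reach.

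**The case against.** The best defence is that this is a coherent design, openly described: one solicited assessment followed by a passive window. Much of that stands, and several stronger readings should be set aside.

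- *A reader might infer that F3 3.e and 3.g contradict each other.* They do not. 3.g offers participants an opportunity to report and does not promise that anyone will ask.
- *A reader might infer that the trial claims 7-day safety.* Neither C2 nor F4 attaches 7 days to the safety outcome. C2 does mention 24 hours, though there the phrase most naturally belongs to pain-medication use, and the two time points in F3 3.d also suggest a short window.
- *A reader might infer that solicited and spontaneous events will be pooled, or that silent participants will count as event-free.* No section says so. G5 says only that missing follow-up will be noted, and tabulation is commonly left to the analysis plan.
- *A reader might infer a bias for or against lidocaine.* Each participant receives both injections and is blinded to side. Nothing in the document suggests that later under-reporting would favour one side; what it shows is a loss of events. A generalised rash could not be assigned to one syringe in any case, so the loss bears mainly on local reactions.
- *A reader might put a number on the missed events.* Any such number is one minus an assumed reporting rate.

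What the defence does not answer is that allergic and injection site reactions are a named outcome, that the protocol itself regards events up to day 7 as reportable, and that nobody is asked about symptoms arising after the survey.

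**Conclusion.** The point holds as a minor weakness in safety ascertainment. The firm result is the schedule: no solicited question for 6 of 7 days, or 5 of 7 for those who answer only the 48-hour email. This assumes that the emails are answered when sent and that participants report everything up to that moment.

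Under-counting of later local or allergic reactions is likely rather than demonstrated. It rests on the ordinary expectation that some events go unreported when nobody asks, and its size cannot be derived from the document. The primary pain outcome is untouched.

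The practical consequence is one of wording. As the plan stands, a statement that no adverse effects were seen would be backed by active questioning for about the first day only.

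**What to change.** 1. Add one automated RedCap email at day 7 that repeats the symptom question. For participants who go on to further injections in a series, ask about symptoms before the next injection, so that events from two treatment occasions are not mixed.
2. In both the 24-hour and the day-7 survey, record left or right for any site reaction. The comparison in G3 and G4 needs this, and it is useful even if the day-7 email is not adopted.
3. Report solicited events separately from spontaneous ones, by time window, and give F3 3.d a category for events after 24 hours.
4. If no day-7 question is added, state in C2 and F4 that the safety conclusion covers the first 24 hours, and list later spontaneous reports separately.

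Cost: one short automated survey in a system already in use, with no extra visit and essentially no extra staff time. The downside is some non-response at day 7, which should be reported with the results. The fallback in item 4 costs only a wording change.

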	3.e 3.f	Reporting ProceduresReporting Procedures	
	3.e	Data Collection Procedures for Adverse Events	11

A Introduction

A1 Study Abstract

There is evidence to suggest that lidocaine can help reduce the pain associated with intramuscular injections of benzathine penicillin G (BPG) or Bicillin, used to treat syphilis infections. A study published in the Journal of Family Practice in 2001 compared the pain experienced during bicillin injections with and without the use of lidocaine. The study found that patients who received lidocaine injections before receiving bicillin reported significantly less pain compared to those who received bicillin injections without lidocaine. Per the International Union against Sexually Transmitted Infections (IUSTI) European Guidelines for syphilis management, lidocaine has been used as a diluent for BPG since 1998. In the United States (US), BPG often comes prepackaged and lidocaine is unable to be used as a diluent with the same ease as it is in Europe. In light of this, we propose a randomized controlled trial of benzathine penicillin G with and without lidocaine to quantify any site pain reduction with lidocaine in patients being treated for syphilis.

This study is a randomized, double blinded, placebo controlled trial. During this study, patients needing BPG treatment for syphilis will be screened for any penicillin allergies and consented to their participation. Each participant will receive 2 injections of BPG, 1.2 million units each (2x1.2 million units = 2.4 million units, the standard dose for syphilis treatment), as intramuscular injections, one in each gluteal muscle, with one of the injections randomly having 0.5ml of 1% lidocaine added while the other has 0.5 ml normal saline solution. The side of each injection will be randomized by the medical assistant (MA)/nurse filling the vials and the injecting MA will be blinded, as well as the study participant, as to which vial contains lidocaine and which contains normal saline. The participants will then be asked to rate their pain from 0-10 on each site of injection at 10 minutes post injection, then again at 24 hours after injection via email electronic survey (via RedCap). The differences in pain from the two injections will be compared and analyzed to see if lidocaine reduces pain associated with BPG injections compared to the control of normal saline added to BPG.

A2 Primary Hypothesis and Purpose of the Study

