This study is comparing standard of care, of not adding lidocaine to prepackaged BPG syringes to the addition of 1% lidocaine, which may relieve pain at injection site. Individuals will receive on injection in each butt cheek, one with lidocaine and one without, and will serve as their own control population. Lidocaine is very commonly used and is quite a low risk medication, and the addition of lidocaine in now way affects the efficacy of BPG.

2.c Subject Recruitment Plans and Consent Process

Participants will be recruited from the Washington University St. Louis Oupatient Infectious Disease Clinic. Each patient who meets the inclusion criteria will be screened by clinic staff and asked if they would consider being a part of this study. They would then be referred to our clinical trials unit upstairs from the WashU Infectious Diseases clinic where they will meet with intake staff via warm handoff and be provided with

information on the study and a consent form. The consent form will be signed prior to the participant being included in the trial as well as any questions required will be answered. Individuals will have between 30-60 minutes to consider participation as they will need to receive treatment prior to them leaving clinic. Any patient will receive standard of care treatment regardless of their willingness to participate in this study and treatment will not be withheld if patients do not participate. Forms will be kept in a secure database via RedCap and treatment will be documented in the participant's chart.

Consent process:

- 1- Participants with confirmed syphilis (RPR and treponemal test positive) who are receiving their first treatment injection of bicillin will be screened for participation in study by infectious diseases clinicians, nurses, or Mas who interact with the patient during their injection visit. If patient is willing to participate, trial team will be notified. (15-30 minutes)
- 2- Trial team will assess patient for inclusion/exclusion criteria and ask if would like to be part of clinical trial. (5 minutes)

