The potential benefit to the participant is that they would receive the treatment they normally would but with the potential benefit of less pain in the injection site with 1% lidocaine. As for the benefit to society, this may provide evidence that may change standard clinical practice with respect to how we perform benzathine penicillin G injections in the US and if lidocaine is shown to cause less pain, then it would become standard practice to include 1% lidocaine in each syringe of benzathine penicillin G.

2.f Early Withdrawal of Subjects, Including When and How to Withdraw Subjects

Early withdrawal of subjects will be handled by the principal investigator, with participants having the direct contact of the PI via email or phone, and through stating that they no longer would like to participate in the study. The PI also will have the right

to withdraw someone if upon evaluation of the patient, they meet certain exclusion criteria. All withdrawals will be done immediately and seeing as this study has short term

of participation, withdrawal should not be difficult.

2.g Data Collection and Follow-up for Withdrawn Subjects

Individuals who withdraw from the study will be noted as lost to follow up and no further data will be obtained from them. They will continue to receive standard of care within the outpatient clinical setting.

E3 Study Drug

3.a Description

1% lidocaine solution added to prefilled 1.2 million units Benzathine penicillin G.

3.b Treatment Regimen

0.5ml 1% lidocaine solution added to prefilled 1.2 million units Benzathine Pencillin G syringe

3.c Method for Assigning Subjects to Treatment Groups

Each participant will receive 2x 1.2 million units injection, one with lidocaine and one with normal saline, therefore each participant will serve as both treatment and control group.

3.d Preparation and Administration of Study Drug

Each syringe of BPG is prefilled. A nurse/MA will then add 0.5 ml 1% lidocaine solution to one BPG syringe, and 0.5ml normal saline solution to another BPG syringe. They will randomly syringes to be injected into the left gluteal muscle vs the right gluteal muscle via random assignment program. They will log the assignment with the unique patient code into a log book.

3.e Subject Compliance Monitoring

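### Each participant is their own control, but G3 and G4 word the tests as a between-group comparison and never commit to a within-person analysis

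*Protocol*

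**What the plan says.** The Protocol describes a split-body design in several places. E2 2.b says participants get two injections, "one with lidocaine and one without, and will serve as their own control population". E3 3.c says "therefore each participant will serve as both treatment and control group", and E3 3.h describes the participant as "serving as their own intervention and control group". F1 step 4 has pain recorded by site: "they will fill out a pain score 0-10 for each injection site at 10 minutes post injection".

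G4 is the methods section, and G3 repeats its sentence: "t-tests or chi-squared tests will be used to compare pain scores and adverse effects between the treatment and control groups". Neither section mentions pairing, within-person differences, McNemar's test, a signed-rank test or a mixed model, and nor does the rest of the Protocol. The nearest statement is in A1: "The differences in pain from the two injections will be compared and analyzed". It points to a within-person comparison but names no test, and G3 and G4 do not carry it over.

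On adverse effects, F4 makes the secondary outcome effects of either drug, "such as allergic reactions or injection site reactions". F2 says the 24-hour survey asks participants "if they had any other symptoms/side effects" and mentions no side. G1 gives 46 patients (92 injections), 80% power and a 0.05 significance level. It does not say which test was assumed and gives no effect size, SD or correlation.

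**The concern.** The two scores to be compared come from the same person, so they are likely to move together: someone who rates pain high tends to do so on both sides. A paired analysis removes that shared component and a two-sample analysis leaves it in the standard error. The text of G3 and G4 permits either. Two analysts could follow it faithfully and report different intervals and p-values for the primary outcome, and one of the two choices could miss a real benefit.

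For adverse effects the problem is of another kind. The sentence plans a comparison by treatment for all of them. A reaction at one injection site can be attributed to lidocaine or saline. A systemic event cannot, because everyone receives both injections at the same visit.

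**Working it through.** **Inputs.** From G1: n = 46 participants (46 pairs), power 80%, significance level 0.05. Two-sided testing is assumed, since G1 does not say. The within-person correlation r is also an assumption; r = 0, 0.3, 0.5 and 0.7 are shown.

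**Step 1: can 46 be reproduced?** No, because G1 gives no effect size or SD. It can only be solved backwards. By the noncentral t distribution at 80% power:
- paired test, 46 pairs: 0.422 SD of the difference;
- two-sample test, 46 per group: 0.590 SD of a single score.

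Either could lie behind 46, so both are carried forward.

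**Step 2: interval width.** With common per-site SD σ, the standard error of the mean difference is σ√(2(1−r)/46) when paired and is estimated as σ√(2/46) when unpaired. The critical values are t(45) = 2.0141 and t(90) = 1.9867, with ratio 0.986. So the width ratio (two-sample to paired) is about 0.986/√(1−r):
- r = 0: 0.99
- r = 0.3: 0.986/0.837 = 1.18
- r = 0.5: 0.986/0.707 = 1.39 (1.40 as a ratio of simulated mean widths)
- r = 0.7: 0.986/0.548 = 1.80

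**Step 3: type I error and power.** These were simulated with 46 bivariate normal pairs and 400,000 trials per setting. In scenario (a) 46 was sized for a paired test, so the true effect in per-site SD units is 0.422 × √(2(1−r)), which is 0.50, 0.42 and 0.33 at r = 0.3, 0.5 and 0.7. In scenario (b) 46 was sized for a two-sample test, so the effect is 0.590.

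| r | Type I error, two-sample | Power (a): two-sample / paired | Power (b): two-sample / paired |
|---|---|---|---|
| 0 | 5.0% | 81% / 80% | 80% / 79% |
| 0.3 | 2.0% | 69% / 80% | 84% / 91% |
| 0.5 | 0.7% | 52% / 80% | 88% / 97.5% |
| 0.7 | about 0.06% | 24% / 80% | 93% / 99.9% |

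The paired test holds its 5% type I error throughout.

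**Step 4: reactions recorded by site.** Both sites were given the same assumed reaction rate, with within-person correlation 0.3, 0.5 and 0.7. Type I error at nominal 5%:

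| Assumed rate | Independent-groups chi-squared | McNemar, asymptotic |
|---|---|---|
| 2% | 0.3%, 0.1%, 0.01% | 0.4%, 0.1%, 0.02% |
| 5% | 2.0%, 0.7%, 0.1% | 3.1%, 1.7%, 0.5% |
| 20–40% | 1.8–2.1%, 0.5–0.7%, 0.04–0.09% | 4.3–4.9% in all cells |

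Exact McNemar is itself conservative, at 0.7–2.8% in the 20–40% rows and lower still at 2–5%.

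**Step 5: systemic events.** No arithmetic applies. Exposure to both lidocaine and saline is 100% in every participant, so there is no treated and untreated set to compare.

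**The case against.** The strongest reply is that the word groups need not mean separate people. E3 3.c uses it for a participant who is both treatment and control, so a comparison between groups can be read as one between a person's two sites. A paired t-test is a t-test, A1 speaks of differences, and E2 2.d and E3 3.e link side, allocation and survey by participant code, which is what a paired analysis needs. The exact variant might be left to an analysis plan that is not at hand. For pain this largely stands. A reader might infer that the Protocol plans an unpaired test, but it never says so. What remains is that its own methods section uses wording that fits the design poorly and leaves the primary test open.

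McNemar's statistic is also referred to a chi-squared distribution, so chi-squared tests is not necessarily the wrong name either. F3 3.d calls events other than injection-site pain rare, although E2 2.e lists edema as common. If reactions are rare, Step 4 shows that the choice of test matters little. That limits the point on site reactions without removing it.

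The reply does not reach systemic events. No reading of G3 and G4 makes a lidocaine-versus-saline comparison of them possible.

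**Conclusion.** The point holds as an ambiguity for pain and as a misfit for adverse effects, and it should be fixed. For pain, the cost arises only if a two-sample test is used and the two scores are positively correlated. Intervals are then about 1.2 to 1.8 times as wide as they need be for r between 0.3 and 0.7. At r = 0 nothing material is lost. The low figure of 24% power needs paired sizing, unpaired analysis and r = 0.7 together.

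Two stronger readings are not supported. A reader might infer a risk of false positives, but under positive correlation the two-sample test errs the other way, with type I error below 5%. A reader might also infer that 46 is the wrong number. G1 does not show its basis, and under two-sample sizing the stated 80% is met by either test when r is positive, so N is not shown to be wrong.

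The results rest on assumed correlations, normal data, two-sided testing and complete pairs.

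**What to change.** In G3 and G4, keep the clause on descriptive statistics and replace only the clause on tests with:

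> At each time point the within-participant difference in pain score (lidocaine site minus saline site) is analysed with a paired t-test and reported as a mean difference with 95% CI. Reactions recorded by injection site are compared within participants with McNemar's test (version stated in advance). Systemic events are summarised descriptively per participant.

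In G1, state whether 46 was calculated for a paired test.

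For pain the cost is wording only, because scores are already taken per site and the log book links side to allocation. It should be done before unblinding. For reactions, the survey form is not shown and F2 only summarises it, so a missing side item cannot be assumed. If side is not recorded, either add one left/right item to the 24-hour survey, a small burden on participants, or describe reactions per participant and drop the comparison by site.
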